APPENDIX IV: FORESEEABLE ADVERSE EVENTS AND ANTICIPATED ADVERSE DEVICE EFFECTS

Access site bleeding event*	Interruption of desired LP function due to electrical interference, either electromyogenic or electromagnetic
Air embolism	Ischemic Stroke
Ateriovenous fistula	Loss of normal device function due to component malfunction
Cardiac arrhythmias	Nausea
Cardiac perforation	Oversensing
Cardiac tamponade	Pacemaker syndrome
Death	Palpitations
Device dislodgement	Pericardial effusion or rub
Dizziness	Pericarditis
Dyspnea	Peripheral nerve damage
Embolization of foreign material	Phrenic nerve/diaphragmatic/extra-cardiac stimulation
Embolism	Pneumothorax/Hemothorax
Endocarditis	Premature battery depletion
Excessive bleeding	Premature deployment with LP migration
Exit block	Premature deployment without LP migration
Failure to capture/loss of capture	Programmer/software anomaly
General surgery risks and complications from comorbidities such as hypotension, hypertension, groin pain, respiratory failure, pneumonia, cardiac failure, reaction to sedation, renal failure/kidney injury, anemia, and death	Pseudoaneurysm formation
Heart Failure	Pulmonary embolism
Helix Distortion	Reaction/Toxic Effect due to contrast media
Hematoma formation, including retroperitoneal hematoma/hemorrhage	RV pacing induced cardiomyopathy
High impedance	Syncope
Hypersensitivity reaction to device materials or substances	Threshold elevation
Inability to disengage snare from docking button	Thromboembolism

Clinical Investigation Plan for Europe

Inability to interrogate or program due to programmer or LP malfunction	Thrombosis
Inability to release and/or redock the LP	Transient ischemic attack
Inadequate Fixation during implant with LP migration	Tricuspid valve damage and/or regurgitation
Inadequate Fixation during implant without LP migration	Undersensing
Inappropriate rate sensor response	Vascular dissection
Infection, local at access site, or systemic	Vascular perforation
Intermittent capture	Vascular puncture
Intermittent or loss of i2i communication	Venous occlusion
Intermittent or loss of sensing	

***Access site bleeding event is defined in section 6.5.1**

A right atriogram and ventriculogram carries risk, most notably, allergic reaction to contrast media.

Clinical Investigation Plan for Europe

APPENDIX V: SIX-MINUTE WALK AND GRADED EXERCISE TEST (CAEP PROTOCOL)

The Aveir atrial LP senses right-atrial blood temperature to provide an increase in pacing rate with increased metabolic demand. The Aveir atrial LP employs algorithms with rate response parameters customized for each patient.

The sensor gain can also be programmed to different settings to adjust the responsiveness of the rate response algorithm and can be optimized for each patient. The programmer has an optimization tool and provides a graphic view of the effects of revised sensor parameter settings on the device's rate response to the patient's exercise during a programming session.

The temperature-based rate response feature in the Aveir atrial LP will be assessed in Aveir DR i2i Study to support the secondary effectiveness endpoint by evaluating whether an appropriate and proportional rate response of the atrial LP in *de novo* subjects can be achieved during a graded exercise test.

It is estimated that a minimum sample size of 8 subjects would be sufficient to evaluate this feature. To ensure that a robust cross-section of subjects is evaluated, however, up to 30 subjects are targeted to undergo this assessment.

Rate Response Protocols

Six Minute Walk Test (6MWT)

All capable subjects at participating centers will be asked to perform a six-minute walk test (6MWT) simulating daily walking activity to identify the appropriate sensor parameters for each subject prior to conducting the graded exercise protocol. The rate response feature should be programmed in AAIR ON or passive mode. Subjects who have an intolerance of high-sensor driven rates are contraindicated for rate-responsive pacing and should not be selected in this assessment. After completion of the 6MWT, the appropriate sensor parameters are to be programmed into the Aveir device and used for the subsequent exercise protocol. The 6MWT may be performed any time after the beginning of the 1-month visit window through the end of the 3-month visit window.

Chronotropic Assessment Exercise Protocol (CAEP)

All capable subjects who completed the 6MWT will be asked to perform the following maximal effort chronotropic assessment exercise protocol (CAEP) to demonstrate an appropriate and proportional response of sensor-indicated rate in graded exercise tests. Subjects who have an intolerance of high-sensor driven rates are contraindicated for rate-responsive pacing and should not be selected for this assessment. The CAEP is designed specifically for chronotropic assessment and is structured to collect heart rate data at submaximal and peak exercise intensities. This protocol has been applied to support mathematical models to describe the normal cardiac chronotropic response to exercise.¹

The CAEP protocol must be performed after completion of the 6MWT protocol and at any time after the beginning of the 3-month visit window through the end of the 6-month visit window. If the 6MWT

Clinical Investigation Plan for Europe

protocol is conducted the same day as the CAEP protocol, subjects are to wait at least 1 hour after the 6MWT protocol has been completed before starting the CAEP protocol.

The CAEP protocol must be administered on a treadmill that could be programmed to the speed and grade/incline settings for each stage of the protocol shown below.

Prior to administration, the Aveir LP rate response settings should be programmed with the same optimized sensor gain that was derived from the 6MWT. However, the physician has discretion to alter these parameters if medically appropriate. The CAEP protocol should be administered the with rate-response feature in **AAIR ON** mode. After a short period of rest, subjects will begin exercise on the treadmill at stage 0 and only progress to the next stage after 2 minutes of exercise. Subjects should be instructed to exercise as long as possible until maximal effort is achieved. Subjects should be instructed to stop if they feel dizzy, chest pain, shortness of breath, fatigue, etc. or any other symptoms. Additionally, at least 5 minutes of rest should be recorded after the patient has ended exercise.

The Chronotropic Assessment Exercise Protocol (CAEP)

Stage	Speed (MPH)	Speed (KPH)	Grade (%)	Time (min)	Cumulative time	METs
0	1.0	1.6	0	2	2	1.5
1	1.0	1.6	2	2	4	2.0
2	1.5	2.4	3	2	6	2.8
3	2.0	3.2	4	2	8	3.6
4	2.5	4.0	5	2/	10	4.6
5	3.0	4.8	6	2	12	5.8
6	3.5	5.6	8	2	14	7.5
7	4.0	6.4	10	2	16	9.6
8	5.0	8.0	10	2	18	12.1
9	6.0	9.7	10	2	20	14.3
10	7.0	11.3	10	2	22	16.5
11	7.0	11.3	15	2	24	19.0

APPENDIX VI: LABELS

Sponsor will provide all implants and accessories with labels stating, “**CAUTION—Exclusively for Clinical Investigation.**” Sponsor will also provide implants and accessories for use in other countries with appropriate country-specific labeling.

Sponsor will provide all implants and catheters as sterile units, and the packaging lists the method of sterilization, manufacturing date, manufacturer name and address, use before date, that devices are single use only, model number, and lot or serial number.

The programmer and accessories’ labels contain the company name, location and phone number, model number, and lot or serial number.

Software versions are displayed on the programmer screen and in printed or saved reports. Validated changes to implant and programmer software are allowed during the study, when necessary, to correct an observed nonconformance with intended device operation.

Leadless implants, catheters and programmers will be stored in a clean, dry, secure location at room temperature prior to shipment to the clinical site.

Copies of all current labeling and Instructions for Use documents for investigational devices listed in Section 2.2.3 will be provided under separate cover to competent authorities and to clinical sites included with other study documentation/information or as part of the Investigator Brochure.

Clinical Investigation Plan for Europe

APPENDIX VII: CASE REPORT FORMS

Final draft case report forms (CRFs) will be provided under a separate cover

Clinical Investigation Plan for Europe**APPENDIX VIII: INFORMED CONSENT FORM**

A template informed consent form will be provided under a separate cover.

Clinical Investigation Plan for Europe

APPENDIX IX: MONITORING PLAN

A copy of the Monitoring Plan can be obtained upon request from the Sponsor Clinical Project Manager for the clinical investigation.

Clinical Investigation Plan for Europe

			[REDACTED] [REDACTED] [REDACTED]	[REDACTED] [REDACTED] [REDACTED]
--	--	--	--	--

Clinical Investigation Plan for Europe

APPENDIX XI: CIP SUMMARY

Clinical Investigation Name and Number	Aveir DR i2i Study ABT-CIP-10428
Title	Aveir Dual-Chamber Leadless i2i IDE Study
Objective(s)	The purpose of this clinical investigation is to evaluate the clinical safety and effectiveness of the Aveir DR LP system in a patient population indicated for DDD(R) pacing to support regulatory pre-market submissions for both DDD(R) and AAI(R) pacing indications in various geographies.
Device Under Investigation	Aveir DR Leadless Pacemaker system
Number of Subjects Required for Inclusion in Clinical Investigation	Up to 550 subjects from up to 85 sites worldwide (United States, Canada, Europe, Asia-Pacific)
Clinical Investigation Design	This is a prospective, multi-center, international, single-arm, pivotal investigational study
Primary Endpoint(s)	
Primary Safety Endpoint: The primary safety endpoint evaluates the 12-month Aveir DR LP system Complication Free Rate (CFR) in de novo subjects based on CEC adjudication of adverse events.
 
Primary Effectiveness Endpoint#1: The primary effectiveness endpoint #1 evaluates the 12-month composite success rate of acceptable atrial pacing thresholds and P-wave amplitudes in de novo subjects.
 
Primary Effectiveness Endpoint#2: The primary effectiveness endpoint #2 evaluates the 3-month AV-synchrony success rate at rest while seated in de novo subjects.

Major (Powered) Secondary Endpoints	
Secondary Safety Endpoint: The secondary safety endpoint evaluates the Aveir Atrial LP complication free rate (CFR) at 12-months post-implant in de novo subjects based on CEC adjudication of adverse events.

Subject Follow-up	
 Baseline, Implant, Pre-discharge, 1-month, 3-month, 6-month, 12-month, and every 6 months thereafter

Clinical Investigation Plan for Europe

Inclusion Criteria	
 1. Subject must have at least one of the clinical indications before device implant in adherence with ACC/AHA/HRS/ESC dual chamber pacing guidelines 2. Subject is \geq 18 years of age or age of legal consent, whichever age is greater 3. Subject has a life expectancy of at least 1 year 4. Subject is willing to comply with clinical investigation procedures and agrees to return to clinic for all required follow-up visits, tests, and exams 5. Subject has been informed of the nature of the clinical investigation, agrees to its provisions and has provided a signed written informed consent, approved by the IRB/EC
Exclusion Criteria	
 1. Subject is currently participating in another clinical investigation that may confound the results of this study as determined by the Sponsor 2. Subject is pregnant or nursing and those who plan pregnancy during the clinical investigation follow-up period 3. Subject has presence of anatomic or comorbid conditions, or other medical, social, or psychological conditions that, in the investigator's opinion, could confound the assessment of the investigational device and/or implant procedure limit the subject's ability to participate in the clinical investigation or to comply with follow-up requirements of the clinical investigation results 4. Subject is a known allergy or hypersensitivity to $<$ 1 mg of dexamethasone sodium phosphate or any blood or tissue contacting material listed in the IFU 5. Subject has an implanted vena cava filter or mechanical tricuspid valve prosthesis 6. Subject has pre-existing, permanent endocardial pacing or defibrillation leads (does not include lead fragments) 7. Subject has current implantation of either conventional or subcutaneous implantable cardioverter defibrillator (ICD) or cardiac resynchronization therapy (CRT) device 8. Subject has an implanted leadless cardiac pacemaker (except for an Aveir ventricular LP) 9. Subject is implanted with an electrically-active implantable medical device with stimulation capabilities (such as neurological or cardiac stimulators) * 10. Subject is unable to read or write 
**NOTE: Does not apply to a medical device with no known impact to the Aveir Leadless Pacemaker System, including the Aveir Link Module. Patient evaluation and the decision to implant the LP should take into account the presence of other active implantable devices and should include consultation with the Sponsor and/or manufacturer of the co-existing device.

Clinical Investigation Plan for Europe

[REDACTED]

- [REDACTED]

- [REDACTED]

- [REDACTED]

This statistical analysis plan (SAP) is intended to provide a detailed and comprehensive description of the planned methodology and analysis to be used for CE mark approval based on ABT-CIP-10428 (CRD 1023), the Aveir DR i2i Study clinical investigation for Europe. This plan is based on the version B of the Clinical Investigation Plan (CIP).

1.2 **Clinical Investigation Objectives**

Primary Objectives

The primary objectives of this study are to evaluate the safety and effectiveness of the Aveir™ Dual-Chamber (DR) Leadless Pacemaker (LP) system through 12-months post-implant in a subject population indicated for a DDD(R) pacemaker system.

Secondary Objectives

The secondary objectives of this study are to evaluate the safety and effectiveness of the Aveir atrial LP through 12-months post-implant in a subject population indicated for a DDD(R) pacemaker system to support an indication for AAI(R) pacing.

1.3 **Clinical Investigation Design**

This is a prospective, multi-center, international, single-arm, pivotal investigational study designed to evaluate the safety and effectiveness of the Aveir DR LP system in a subject population indicated for a DDD(R) pacemaker.

The clinical investigation will enroll up to 550 subjects from up to 85 participating centers from the United States, Canada, Europe, and Asia Pacific. The Sponsor may approach centers in other countries for participation in the clinical investigation as needed.

Subjects participating in the clinical investigation will be followed through at least 12 months with data collected at baseline, implant procedure, pre (hospital) discharge, and follow-up at 1 month, 3 months, 6 months, 12 months and every 6 months thereafter until study completion.

1.4 **Endpoints**

The primary and secondary endpoint analyses will be based on newly enrolled (*de novo*) subjects in the investigation who have an attempted implant. *De novo* subjects are defined as subjects that do not have an implanted pacemaker on the date of consent through the date of the Aveir LP implant.

The Aveir DR i2i Study for Europe will include the following endpoints.

Statistical Analysis Plan

1.4.1 Primary Safety Endpoint

The primary safety endpoint evaluates the 12-month Aveir DR LP system Complication Free Rate (CFR) in *de novo* subjects based on CEC adjudication of adverse events.

1.4.2 Primary Effectiveness Endpoint #1

The primary effectiveness endpoint #1 evaluates the 12-month composite success rate evaluating acceptable atrial pacing thresholds and P-wave amplitudes in *de novo* subjects.

1.4.3 Primary Effectiveness Endpoint #2

The primary effectiveness endpoint #2 evaluates the 3-month AV synchrony success rate at rest while seated in *de novo* subjects.

1.4.4 Secondary Safety Endpoint

The secondary safety endpoint evaluates the 12-month Atrial LP CFR in *de novo* subjects based on CEC adjudication of adverse events.

1.4.5 Secondary Effectiveness Endpoint

The secondary effectiveness endpoint evaluates the appropriate and proportional rate response of the atrial LP in *de novo* subjects during graded exercise testing (CAEP protocol).

1.5 Randomization

Not Applicable.

1.6 Blinding

Not Applicable.

2.0 ANALYSIS CONSIDERATIONS

2.1 Analysis Populations

The analysis populations include:

2.1.1 Full Analysis Population

Full Analysis population includes all subjects who have an attempted implant. An implant is considered attempted when the Aveir Introducer Sheath or Aveir dilator is inserted through the skin of the access site.

[REDACTED]

[REDACTED]

Statistical Analysis Plan

2.2 Statistical Methods

For the primary and secondary endpoints, hypothesis tests will be performed. In addition, a set of additional data will be summarized by descriptive statistics or Kaplan-Meier analysis.

2.2.1 Descriptive Statistics for Continuous Variables

For continuous variables (e.g., age, etc.), results will be summarized with the numbers of observations, means, and standard deviations, with quartiles, minimums, maximums, and 95% confidence intervals for the means as per the table mockups.

2.2.2 Descriptive Statistics for Categorical Variables

For categorical variables (e.g. gender, cardiac disease history, etc.), results will be summarized with subject counts and percentages/rates, and where specified in the table mockups, with exact 95% Clopper-Pearson confidence intervals.

2.2.3 Survival Analyses

For time-to-event variables, Kaplan-Meier analysis will be conducted. Subjects without events will be censored at their last known event-free time point, and for subjects with events the time to the first event will be used for the analysis. Survival estimates of the data and associated 95% confidence interval will be presented using cumulative survival and its estimated standard error (Greenwood's formula).

2.3 Endpoint Analysis

The primary and secondary endpoint analysis will be based on the newly enrolled (de novo) subjects in the study.

2.3.1 Primary Safety Endpoint Analysis

The primary safety endpoint evaluates the 12-month Aveir DR LP system CFR based on CEC adjudication of adverse events. A complication is defined as a device-or procedure-related serious adverse event (SADE), including those that prevent initial implantation (includes both Atrial LP and Ventricular LP complications and implant procedure-related complications).

The primary safety endpoint hypothesis is:

$H_0: CFR \leq 76.5\%$ vs. $H_1: CFR > 76.5\%$

where 76.5% is the performance goal (PG).

The CFR at 12 months will be estimated using the Kaplan-Meier survival analysis. The associated one-sided lower 97.5% confidence interval will also be provided (using the Greenwood variance estimates). The null hypothesis is rejected at the 2.5% significance level if the LCB exceeds the PG of 76.5%. The p-value from the one-sided Z-test will be calculated and compared to the 2.5% significance level.

The primary analysis population for the primary safety endpoint analysis will be based on subjects in the full analysis population.

Statistical Analysis Plan

To eliminate the possible impact of Covid-19 on the confirmatory safety endpoint analysis, CEC adjudicated primary safety events (SADEs) that are related or possibly related to Covid-19 will be excluded from the primary safety endpoint analysis. Subjects who have these events will be censored at the time of the event. Additional analysis with these events included will also be provided.

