A complication is defined as a device-or-procedure-related serious adverse event (SADE), including those that prevent initial implantation (includes both Atrial LP and Ventricular LP related complications and implant procedure-related complications).

4.1.1.1 **Rationale for Selection of the Primary Safety Endpoint**

The primary safety endpoint evaluates a device- or procedure-related SADE rate which is an appropriate measure for safety and consistent with the primary safety endpoints used in the Leadless II IDE trial (Phase 1: NCT02030418 and Phase 2: NCT04559945) and multiple pre-market leadless pacemaker trials. The 12-month follow-up period for the primary safety endpoint analysis is consistent with the minimum follow-up duration for CE-approved trials

Clinical Investigation Plan for Europe

recommended in the MHRA Leadless Expert Advisory Guidance document.¹⁷ In addition, The 12-month timepoint for assessing the primary safety endpoint is an appropriate time period as outlined in FDA's Executive Summary on leadless pacemaker devices (February 2016): "based on publicly available clinical data for leadless pacemaker devices, it is known that the overwhelming majority of complications occur within 30 days, most within 14 days".⁸ In the Leadless II IDE study, all SADEs for the primary safety endpoint analysis occurred within the 30-day early post-procedure period.⁹

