4.1.4 Secondary Safety Endpoint

The secondary safety endpoint evaluates the 12-month Aveir atrial LP complication free rate in *de novo* subjects based on CEC adjudication of adverse events.

An atrial LP complication is defined as an atrial device- or procedure-related SADE, including those that prevent initial LP implantation. Complications that are exclusively related to the ventricular LP or its delivery/retrieval will not be considered atrial LP complications and will be excluded from this evaluation. Complications that cannot be exclusively determined to be related to the ventricular or atrial LP will be considered atrial LP complications (e.g. femoral access complications, embolism, etc.).

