2.3.4 Secondary Safety Endpoint Analysis

The secondary safety endpoint evaluates the 12-month Aveir atrial LP related CFR_A based on the CEC adjudication of adverse events. The secondary safety endpoint will be tested if all the primary endpoints are met.

An atrial LP complication is defined as an atrial device- or procedure-related SADE, including those that prevent initial LP implantation. Complications that are exclusively related to the ventricular LP or its delivery/retrieval will not be considered atrial LP complications and will be excluded from this evaluation. Complications that cannot be exclusively determined to be related to the ventricular or atrial LP will be considered atrial LP complications (e.g. femoral access complications, embolism, etc.). The secondary safety endpoint hypothesis is:

H₀: CFR_A ≤ 82% vs. H₁: CFR_A > 82%

where 82% is the PG.

The CFR_A at 12 months will be calculated using the Kaplan-Meier survival analysis. The associated one-sided lower 97.5% confidence interval will also be provided (using the Greenwood variance estimates). The null hypothesis is rejected at the 2.5% significance level if the LCB exceeds the PG of 82%. The p-value from the one-sided Z-test will be calculated and compared to the 2.5% significance level.

The secondary safety endpoint analysis will be based on the subjects in the full analysis population.

To eliminate the possible impact of Covid-19 on the confirmatory safety endpoint analysis, CEC adjudicated primary safety events (SADEs) that are related or possibly related to Covid-19 will be excluded. Subjects who have these events will be censored at the time of the event. Additional analysis with these events included will also be provided.

Statistical Analysis Plan

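### Both confirmatory safety tests leave out adjudicated SADEs related or possibly related to Covid-19, a rule that for any counted event can only help the device; the all-events analysis, already planned as additional, should be the confirmatory one

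*SAP*

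**What the plan says.** CIP 4.1.1 defines the primary safety event: "A complication is defined as a device-or-procedure-related serious adverse event (SADE), including those that prevent initial implantation". CIP 4.1.4 defines the atrial one: "An atrial LP complication is defined as an atrial device- or procedure-related SADE, including those that prevent initial LP implantation". CIP 8.2.1 and 8.2.4 repeat these definitions. None of the four sections mentions Covid-19 in its visible text.

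SAP 2.3.1 repeats the primary definition and then adds that "CEC adjudicated primary safety events (SADEs) that are related or possibly related to Covid-19 will be excluded from the primary safety endpoint analysis", with the aim of removing the pandemic's influence from the confirmatory analysis. SAP 2.3.4 has the matching rule for the atrial test and, like 2.3.1, specifies the handling: "Subjects who have these events will be censored at the time of the event". Both sections add: "Additional analysis with these events included will also be provided".

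Three other provisions matter here:
- SAP 2.2.3 sets the time scale: "for subjects with events the time to the first event will be used for the analysis".
- CIP 7.2.1 has the investigator judge the Covid-19 relation of each adverse event. When a relation is found, the investigator must complete a log confirming a positive test. The section does not link this to the endpoint.
- CIP 3.2 says that the primary safety analysis uses the CEC's adjudication alone.

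**The concern.** The rule does not filter background illness. It acts on events already judged serious and device- or procedure-related, and takes some of them out of the pass/fail test because Covid-19 is related or may be. An event can be possibly Covid-19 related and still be a complication of the device or procedure. The formal test therefore covers fewer events than the CIP endpoint, and the analysis that matches the CIP definition has only a supporting role.

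The removal works in one direction. Read literally, it also reaches further than the flagged event: once the subject is censored, a later complication with no Covid-19 link is lost as well. The primary result also opens the atrial test ("The secondary safety endpoint will be tested if all the primary endpoints are met"), so a primary pass that depends on exclusions would carry forward.

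The SAP does not say whose judgement of the Covid-19 relation triggers the exclusion, the CEC's or the investigator's under CIP 7.2.1.

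**Working it through.** **Inputs.** N = 300 for both safety tests (CIP 8.3, SAP 2.4). Goals 76.5% and 82%, one-sided 2.5%, Kaplan-Meier with Greenwood variance (SAP 2.3.1, 2.3.4). Atrial planning rate 90% (CIP 8.3). The primary planning rate and both powers are redacted, so there is no stated power to reproduce. For orientation, the atrial test at 90% has approximate power Φ(0.08/√(0.9×0.1/300) − 1.96) = Φ(4.62 − 1.96) = 99.6%.

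**Step 1, direction.** S = Π(1 − d/n), G = Σ d/[n(n − d)], lower bound = S(1 − 1.96√G). If one of the d events at time t becomes a censoring at t, that factor rises from 1 − d/n to 1 − (d − 1)/n. The subject leaves the risk set after t either way, so later risk sets do not change. S rises and G falls, so the lower bound rises. In 1,801 simulated changes neither the CFR nor the bound ever fell.

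One small exception lies outside this argument. SAP 2.3.4 refers to primary safety events. Taken literally, a subject with a Covid-19-related SADE of the ventricular device only would be censored while still event-free for the atrial endpoint. With 30 atrial events in 300, one such early censoring moves the atrial CFR from 90.00% to 89.97%.

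**Step 2, boundary cases.** Without other censoring the bound is p − 1.96√(p(1 − p)/300).
- Primary, 57 events: p = 243/300 = 81.00%, bound 76.56%, pass.
- Primary, 58 events: p = 242/300 = 80.67%, bound 76.20%, fail.
- Atrial, 42 events: p = 258/300 = 86.00%, bound 82.07%, pass.
- Atrial, 43 events: p = 257/300 = 85.67%, bound 81.70%, fail.

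Next, exclusions were applied at every position among untied event times:
- 58 primary events, one excluded: bound 76.48–76.56%. It still fails if the excluded event is among the first 15 in time and passes otherwise.
- 58 primary events, any two excluded: bound 76.77–76.92%, always a pass.
- 43 atrial events, any one excluded: bound 82.01–82.07%, always a pass.

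Each single exclusion raises the CFR by 0.27 to 0.33 points.

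**Step 3, paired simulation.** Each data set was tested both ways. Assumptions: N = 300; 90% of events uniform over days 0–30 and the rest uniform to day 365; 10% drop-out uniform over the year; each observed event flagged with probability 2% or 5%; 20,000 data sets per setting. The timing reflects CIP 4.1.1.1 ("the overwhelming majority of complications occur within 30 days, most within 14 days"). The flagged shares, and the true rates of 80% and 85%, are illustrations that do not come from the documents.

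| Test and true CFR | 2% flagged: all events → SAP rule | 5% flagged: all events → SAP rule |
|---|---|---|
| Primary, 76.5% (at goal) | 3.2 → 4.6% | 3.1 → 7.5% |
| Primary, 80% | 34 → 40% | 34 → 49% |
| Primary, 85% | 96.9 → 97.8% | 97.0 → 98.7% |
| Atrial, 82% (at goal) | 3.2 → 4.5% | 3.3 → 7.1% |
| Atrial, 90% | 98.7 → 99.0% | 98.7 → 99.4% |

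The true CFR here is the CIP-defined one, with all events counted. The atrial rows stand alone and ignore the gate from the primary tests. At the primary goal, 2% and 5% flagged mean about 1.4 and 3.5 exclusions per trial. No data set went from pass to fail. The baselines above 2.5% come from the normal-approximation bound, not from the Covid-19 rule. Repeat runs agreed to within 0.5 points.

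**The case against.** The strongest reply is that this is a choice of label. The rule, its purpose, the censoring method and the all-events analysis are all written down in advance. An independent committee adjudicates the events, and CIP 7.2.1 asks for a confirmed positive test when the investigator finds a Covid-19 relation. An event must be serious, device- or procedure-related and at least possibly Covid-19 related, and most complications fall in a short early window, so few may qualify. At the only visible planning rate the effect is under one percentage point.

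Much of this stands. A reader might infer that the SAP contradicts the CIP, but CIP 8.0 leaves analysis detail to the SAP, and silence on Covid-19 is not a conflict. A reader might also infer that complications are hidden, or that only doubtful links are removed. The all-events result will be reported, and the rule covers related as well as possibly related events. The success and multiplicity sections (SAP 2.7, 2.10) are redacted, so any further role for the all-events result cannot be seen. The basis of the performance goals is not visible either, so it cannot be judged whether the exclusion helps or harms comparability with them.

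The reply does not answer the main point. Which CIP-defined complications count in the pass/fail test is more than detail, and the narrowing favours the device. The positive-test log does not settle the matter, because the SAP does not tie the exclusion to it. If few events are flagged, counting them costs the sponsor almost nothing.

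**Conclusion.** The concern holds in limited form. Both confirmatory safety tests omit events that meet the CIP definition of a complication, and for any counted event the omission raises the CFR and its lower bound and never lowers them. Near the goals, one or two exclusions can change the result. If 5% of events were flagged, the false-pass rate against the CIP-defined CFR would roughly double. Well above the goals the effect is negligible.

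These sizes rest on N = 300, full follow-up in the boundary cases, and assumed flagging shares and event timing in the simulation. The documents give no expected number of flagged events, and the primary planning rate is redacted. A reader might conclude that the trial is likely to pass because of this rule; nothing in the documents supports that. It is a change the plan should make, not a defect that invalidates the design.

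**What to change.** In SAP 2.3.1 and 2.3.4, swap the roles of the two analyses. Suggested wording: *The confirmatory analysis counts all CEC-adjudicated SADEs that meet the endpoint definition, regardless of any relation to Covid-19. A supportive analysis excludes those that the CEC adjudicates as related or possibly related to Covid-19, censoring the subject at the event. The number of such events and subjects is reported.* In 2.3.4, refer to atrial complications rather than primary safety events. The supportive analysis still serves the SAP's aim of showing the result without pandemic influence.

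The cost is SAP wording, plus a CEC decision on Covid-19 relation where that is not already collected. The reported CFR may be about 0.3 points lower per affected subject. The chance of passing falls slightly: in the simulation at a true atrial CFR of 90%, it is 98.7% instead of 99.0–99.4%.
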